3.5 Exposure

Metabolites of intestinal probiotics are those bioactive compounds produced by intestinal bacteria when they consume prebiotics, including short-chain fatty acid, lipolyaccharide, enzyme, exopolysaccharide, cell-free supernatant, inactivated probiotic bacteria or cell fragments (e.g. cell wall fragments, bacterial lysates, et al) and other metabolites (e.g. vitamins, amino acids, et al). Supplying exogenous

intestinal probiotic metabolites is one of the therapies for intestinal flora disorder. It can regulate intestinal flora, improve nutritional status, reduce serum levels of urotoxins and improve quality of life. Patients usually need 8-12 weeks to take the postbiotic product. Here is the introduction of postbiotic product.

The **Postbiotics** used in this study is Yi'en Yuan Honey Fermented Drink, which is made from water, edible brown sugar, and honey as raw materials. It is fermented by a mixture of plant lactic acid bacteria and coagulating Bacillus, and then inactivated at high temperature. The production of the product follows the GB7101 standard, and no live bacteria or related prohibited ingredients are detected in the finished product, which meets the food and beverage standards. According to *NJ-W22070721 Yi'en Yuan Honey Fermented Drink* and *SH-W23040315 Honey enzyme beverage test report*, the product includes carbohydrate 4.0-4.7g/100mL, potassium about 60.9mg/100mL, phosphorus about 2.8mg/mL. According to the concentration shown above, if you consume 150ml of the product a day, you will intake carbohydrate 6.0-9.1g, potassium 90mg, phosphorus 4.2mg, which is far lower than the daily intake of these substances from the diet and can be used for dialysis and diabetic patients. Since its launch in June 2021, no side effects have been reported.

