3.4 Outcomes

3.4.1 Primary Outcome Measure:

Outcome Measure	Measure Description	Time Frame
Changes of nutritional status from the baseline to the end of treatment and differences between the intervention group and the placebo group.	Nutritional status of the patient is defined as the results of physical examination and SGA-7 rating scale.	From the baseline to the end of treatment.
Changes of quality of life from the baseline to the end of treatment and differences between the intervention group and the placebo group.	Quality of life of the patient is defined as the scores of gastrointestinal symptom rating scale (GSRS), kidney disease life quality scale (TM-SF36) and enervation frailty scale (EFS).	From the baseline to the end of treatment.

3.4.2 Secondary Outcomes:

Outcome Measure	Measure Description	Time Frame
Changes of enterogenous urotoxin level from baseline to the end of treatment and difference between the intervention and placebo group.	Enterogenous urotoxin level is defined as the serum level of IS, PCS and TMAO. The levels of serum IS, PCS and TMAO will be measured by mass spectrometry.	From the baseline to the end of treatment.

Changes of intestinal flora structure from the baseline to the end of treatment, and the difference between the intervention group and the placebo group.
	
The structure of intestinal flora will be measured by the V3-V4 region of 16S rDNA with MiSeq PE300 sequencing platform for high-throughput analysis and described by number of the flora.
	
From the baseline to the end of treatment.

Changes of routine biochemical indicators from the baseline to the end of treatment, and differences between the intervention group and the placebo group.
	
The routine biochemical indicators include serum creatinine, urea nitrogen, albumin, prealbumin, hemoglobin, serum calcium, blood phosphorus, total parathyroid hormone, serum potassium, carbon dioxide, C-reactive protein, ferritin, transferrin saturation.
	
From the baseline to the end of treatment.

Changes of dietary intake from the baseline to the end of treatment, and the difference between the intervention group and the placebo group.
	
Dietary intakes of the patients will be described by the diet record.
	
From the baseline to the end of treatment.

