4.1 Subject Benefit

The study is a crossed randomized control study of metabolites from the gut microbiota and every patient enrolled in the study will receive free use of intestinal probiotic metabolites. The study will provide the relevant test, nutrition and quality of life evaluation free of charge. The examinations in the study are all routine examinations in daily clinical work and do not increase the burden of blood collection for patients. The only invasive test is venous blood sampling for urotoxins measurement, which is carried out according to the routine procedure. The patient needs to collect a stool sample for microflora measurement. The other tests and evaluations are non-invasive.

Regular treatment will not be affected for the patients who do not accept the study. The privacy information of all patients entering the study will be protected and the data will be used in accordance with relevant regulations.

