4.2 Subject Risk

During the trial, the treatment group will take 150ml of Yi En Yuan honey yeast drink each day. The product is made of water, edible brown sugar and honey. It's mixed fermented by plant lactic acid bacteria and Bacillus coagulates and sterilized at a high temperature. The product is produced according to GB7101 standard, and there is no live bacteria and prohibited ingredients in the product, which meets the food and beverage standards. According to *NJ-W22070721 Yi En Yuan honey yeast drink* and *SH-W23040315 Honey enzyme beverage test report*, the product includes carbohydrate 4.0-4.7g/100mL, potassium about 60.9mg/100mL, phosphorus about 2.8mg/mL. According to the concentration shown above, if you consume 150ml of the product a day, you will intake carbohydrate 6.0-9.1g, potassium 90mg, phosphorus 4.2mg, which is far lower than the daily intake of these substances from the diet and can be used for dialysis and diabetic patients. Since its launch in June 2021, no side effects have been reported. Patients in the control group will be given 150ml of placebo each day which is made of water and food coloring.

Blood samples of the subjects are taken at the same time as routine clinical tests without additional samples. The risks are the same as those in daily blood drawing tests, including puncture pain, the need for a second puncture when the blood drawing is not successful, and a small amount of subcutaneous bleeding caused by poor compression after blood drawing. Blood drawing will be performed by experienced nurses. The venous blood collection routine will be strictly followed, and after blood

collection we will press effectively to stop bleeding. If the puncture is unsuccessful, we will stop the second puncture and we will try again after 24 hours.

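### The stated daily phosphorus intake (4.2 mg) is one hundredth of what the stated concentration gives for 150 mL (420 mg), and the carbohydrate ceiling does not follow from its concentration either

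*Protocol*

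**What the plan says.** Section 3.5 (Exposure) gives the composition of the drink as "the product includes carbohydrate 4.0-4.7g/100mL, potassium about 60.9mg/100mL, phosphorus about 2.8mg/mL", citing two named test reports. It continues: "According to the concentration shown above, if you consume 150ml of the product a day, you will intake carbohydrate 6.0-9.1g, potassium 90mg, phosphorus 4.2mg". Section 4.2 (Subject Risk) repeats the same concentrations and intakes and draws the same conclusion about them: "which is far lower than the daily intake of these substances from the diet and can be used for dialysis and diabetic patients".

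The volume is the actual study volume: "During the trial, the treatment group will take 150ml of Yi En Yuan honey yeast drink each day". The comparator contains none of these constituents by description: "Patients in the control group will be given 150ml of placebo each day which is made of water and food coloring". Section 4.1 adds that "every patient enrolled in the study will receive free use of intestinal probiotic metabolites"; group B is to receive the drink in weeks 13 to 24.

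Serum phosphorus is also an outcome. Section 3.4.2 lists it among the biochemical measures compared between arms: "The routine biochemical indicators include serum creatinine, urea nitrogen, albumin, prealbumin, hemoglobin, serum calcium, blood phosphorus, total parathyroid hormone".

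**The concern.** The protocol presents the daily intakes as a direct product of concentration and volume, so a reader can check them in one line. For phosphorus the check fails by two orders of magnitude, and for the upper carbohydrate value it fails by more than rounding. Sections 3.5 and 4.2 agree with each other. The contradiction lies inside each section, between the concentration and the intake said to follow from it.

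These intakes are the only numbers the protocol offers for judging the drink acceptable in people on hemodialysis, and they stand in the section that describes risk to subjects. If the concentration is right as printed, that section understates daily phosphorus 100-fold. If the intake is right, only the unit is wrong and the conclusion keeps its basis. A reader cannot tell which applies.

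There is a smaller consequence for interpretation. Serum phosphorus is compared with a placebo of colored water, so the phosphorus content of the active product would be needed to explain any difference between arms.

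**Working it through.** **Inputs, all from section 3.5 and repeated in 4.2**

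- Carbohydrate 4.0-4.7 g/100 mL; potassium 60.9 mg/100 mL; phosphorus 2.8 mg/mL.
- Daily volume 150 mL, which 4.2 also gives as the treatment group's volume.
- Stated intakes: carbohydrate 6.0-9.1 g, potassium 90 mg, phosphorus 4.2 mg.

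**Formula.** Daily intake = concentration × 150 mL. For a concentration per 100 mL, this means multiplying by 1.5.

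**Figures that reproduce**

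- Carbohydrate, lower end: 4.0 × 1.5 = 6.0 g. Stated 6.0 g.
- Potassium: 60.9 × 1.5 = 91.35 mg. Stated 90 mg, which is 1.5% lower and consistent with rounding.

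These two confirm that the formula is the one the protocol used.

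**Figures that do not reproduce**

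| Constituent | Calculation | Result | Stated | Ratio |
|---|---|---|---|---|
| Phosphorus, unit as printed | 2.8 mg/mL × 150 mL | 420 mg | 4.2 mg | 420 / 4.2 = 100 |
| Carbohydrate, upper end | 4.7 g/100 mL × 1.5 | 7.05 g | 9.1 g | 9.1 / 7.05 = 1.29 |

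**What would make the stated figures true**

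- Phosphorus: 2.8 mg per 100 mL × 1.5 = 4.2 mg exactly. With the printed unit, 4.2 mg corresponds to 4.2 / 2.8 = 1.5 mL of drink a day.
- Carbohydrate: 9.1 g in 150 mL needs 9.1 / 1.5 = 6.07 g/100 mL, above the stated range. Alternatively, at 4.7 g/100 mL it needs 9.1 / 4.7 × 100 = about 194 mL.

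**Scale of the two phosphorus readings.** As printed, 2.8 mg/mL is 280 mg/100 mL, which is 280 / 60.9 = 4.6 times the stated potassium concentration. Read per 100 mL, it is 2.8 / 60.9 = 0.046 times potassium.

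**The case against.** The best reply is that this is a missing 100 in one unit. The two neighboring constituents are given per 100 mL, 2.8 × 1.5 is exactly 4.2, and nothing in the protocol favors the 420 mg reading. The safety sentence rests on the intake, not on the concentration, so on this reading the conclusion stands and the factor of 100 measures a mismatch rather than a demonstrated exposure. This is the likeliest explanation. It remains an inference, because the test reports that would settle it are cited but not reproduced.

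Several further points limit the weight of the finding, and they stand:

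- The protocol gives no figure for dietary phosphorus, so the document alone cannot show whether its comparison with dietary intake would fail even at 420 mg.
- The carbohydrate ceiling errs high if the listed range is right, so it does not weaken the safety statement.
- Serum phosphorus is one of 13 indicators within a secondary outcome, and the randomized comparison estimates the drink's effect whatever its labeled content. Correct content helps explain a result; it is not needed to obtain one.
- Exposure of all 2 × 30 = 60 planned patients is an upper bound. Group B receives the drink only from week 13, and removals and 20% dropout are expected.
- Serum phosphorus is scheduled at baseline and every 4 weeks, so a large effect would probably be noticed.

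None of these points makes the printed figures consistent.

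**Conclusion.** The protocol is wrong as written in both sections. The printed phosphorus concentration and daily intake cannot both hold for 150 mL: the concentration implies 420 mg, and the intake is given as 4.2 mg. The upper carbohydrate value is 9.1 - 7.05 = 2.05 g (29%) above what the stated range allows. Potassium is not in question.

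The conclusion rests only on the printed concentrations, the printed volume and multiplication. It does not establish which phosphorus figure is wrong. If the unit should be per 100 mL, this is a unit error with no change in exposure. If the printed unit is right, Subject Risk understates daily phosphorus 100-fold. Because the text supports a suitability statement for dialysis patients, it should be corrected even though the harmless reading is the more likely one. The carbohydrate discrepancy is minor and matters mainly as a sign that the paragraph was not checked against its own inputs.

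**What to change.** 1. Check the phosphorus and carbohydrate concentrations, with their units, against the two test reports named in sections 3.5 and 4.2.
2. Recompute the intakes for 150 mL from the confirmed values, and correct whichever printed figures are wrong in both sections, so that each intake follows from its concentration.
3. Once the phosphorus figure is confirmed, re-check the sentence comparing intake with the diet and stating suitability for dialysis and diabetic patients, and state the dietary figure used for the comparison.
4. Carry any correction into subject information, if it repeats these numbers.

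The cost is a check of two existing reports and corrected wording in two sections. Design, outcomes, sample size and analysis do not change.

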3.6 Sample Size

The study is a randomized control trial. There is no previous related published study so that it's an exploratory trial. According to the study of other micro ecological preparations, the sample size of each group should be 20. Taking into consideration the dropout rate of 20% by the end of the study, a sample size of 30 per group is planned for this study.

3.7 Data Management

The clinical questionnaire is designed by the doctor whose professional position is or above the associate director. The clinical data is collected and entered by the clinical graduate students participating in the study, while another graduate student verifications the data to ensure the reliability and effectiveness. Each subject is coded by a unique number for subsequent analysis. The clinical data will be encrypted, stored and backed up, and the data analysts should consider of timely updating and integrity. The tests involved in the study are routine clinical tests for MHD patients, and the relevant clinical departments will perform the data entry and storage. The relevant data will be saved by the hemodialysis researchers of the Department of Nephrology, Peking University First Hospital.

The scales involved in the study are commonly used in clinical fields and have been widely used in hemodialysis population. The kidney disease quality of life scale will be completed by the subjects themselves.

3.8 Statistical Analysis

Descriptive statistics for continuous variables will include questionnaire score, anthropometric and biochemical indicators, fecal flora structure and urotoxins level. They will be expressed as mean \pm standard deviation and median. Analysis of categorical variables will include frequency and percentage.

In analytical statistics, the distribution type of data will be initially considered when we determine the reference range, and then we will calculate the unilateral lower limit P5. We will compare the distribution of the variables between the normal population and the patients in the two groups with Independent t test, Chi-square test /Fisher exact test, one-way ANOVA and non-parametric analysis. We will analyze the relationship between exposure and outcome with Logistic regression and Cox

regression, including univariate and multivariate regression. In multivariate regression analysis, the selected variables include important general clinical data, the variables clearly associated with the outcome, and the variables analyzed as $P < 0.1$ in univariate regression.

Statistical analyses will be performed using Statistical Package for Social Science (SPSS) for Windows version 23.0 (SPSS Inc. Chicago, IL). Statistical mapping will be performed using GraphPad Prism v.8 (La Jolla, CA, USA) and R 4.1.0 (The R Foundation, Vienna, Austria). Sample size estimation will be performed using PASS 2021 (UT, USA).

$P < 0.05$ is considered statistically significant. All confidence intervals are stated at the 95% confidence level.

4. Subject Protection

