3.1 Design

The study is a multicenter prospective open labeled randomized controlled trial. Elderly patients with age ≥ 65 years and received hemodialysis treatment for more than 6 months will be included in the study. After enrollment, the patients will be educated about how to keep diet records and then they will be randomly divided into group A and group B in a 1:1 ratio. The patients in group A will receive oral postbiotics and group B receive placebo. The treatment period is 12 weeks. Subsequently, group A ends the trial, and group B enters the remedial treatment period, receiving oral postbiotics, and the treatment cycle is 12 weeks. At 0, 12th and 24th week, quality of life score, nutrition evaluation, diet status and gastrointestinal symptom score of patients will be evaluated. The stool and serum of patients will be collected for intestinal flora and urotoxins IS, PCS and TMAO measurements. The improvement of biochemical indicators will be evaluated. The biochemical indicators include blood creatinine, urea nitrogen, albumin, prealbumin, hemoglobin, blood calcium, blood phosphorus, whole parathyroid hormone, blood potassium, C-reactive protein, ferritin, transferrin saturation, et al. During the whole intervention process, patients will be encouraged to maintain intake of protein and fiber and keep a diet log.

During the intervention process, the process of hemodialysis and other diagnosis and treatment behaviors will be performed according to clinical routine.

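### Section 3.8 never clearly states the A-versus-B comparison of change that 3.4.1 makes primary; it names an unsourced normal population and a Cox model with no event

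*Protocol*

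**What the plan says.** **Primary contrast (Protocol 3.4.1).** The two primary outcomes are "Changes of nutritional status from the baseline to the end of treatment and differences between the intervention group and the placebo group" and "Changes of quality of life from the baseline to the end of treatment and differences between the intervention group and the placebo group". The measures are the physical examination and SGA-7 for nutrition, and GSRS, TM-SF36 and EFS for quality of life.

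**Population (3.1).** Elderly patients who "received hemodialysis treatment for more than 6 months will be included in the study" are randomised 1:1 to postbiotics (group A) or placebo (group B). The inclusion criteria in 3.3.1 likewise admit only maintenance haemodialysis patients.

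**Analysis (3.8).**
- A reference range is planned, "and then we will calculate the unilateral lower limit P5".
- The group comparison reads "We will compare the distribution of the variables between the normal population and the patients in the two groups with Independent t test". The list of tests goes on to chi-square or Fisher, "one-way ANOVA and non-parametric analysis".
- For modelling: "We will analyze the relationship between exposure and outcome with Logistic regression and Cox" regression.
- Covariates for the multivariate models include important clinical data, variables clearly associated with the outcome, and "the variables analyzed as $P < 0.1$ in univariate regression".

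**The concern.** The analysis section should say how the primary contrast will be estimated. Here its comparison sentence brings in a group that the trial does not have, and its modelling sentence includes a method for which the trial has no outcome. No sentence in 3.8 mentions change from baseline or sets A against B.

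An SAP that followed 3.8 faithfully would not answer the question in 3.4.1. An SAP that answered it would depart from the protocol. Either way, the analysis supporting the main conclusion would be settled outside the protocol, in a trial described as open label in 3.1, where it is especially useful to have the primary comparison fixed in advance.

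**Working it through.** No figure in the protocol is in dispute, so the check sets the sections side by side.

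1. **Who supplies data?** 3.1 and 3.3.1 admit only haemodialysis patients aged 65 or over. 5.2 takes blood before dialysis from the subjects. Two groups supply data, A and B. No healthy cohort, normative data set or external reference sample is described anywhere. The normal population in 3.8 therefore has no source.

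2. **Is the P5 limit used?** 3.4 has two primary and four secondary entries (2 + 4 = 6). All six are worded as a change from baseline to end of treatment and a difference between intervention and placebo. None is defined by falling below a reference limit. A P5 could be computed, but it feeds no outcome.

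3. **Does Cox regression have a response?** The six entries cover physical examination and SGA-7, quality-of-life scales, serum toxins, intestinal flora, routine biochemistry, and diet. Time-to-event outcomes: 0 of 6. No event or censoring rule is given.

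4. **Does the exposure-and-outcome sentence supply the A-versus-B contrast?** Section 3.5 is headed Exposure and describes the postbiotic, so the sentence can be read as treated versus control. The models it names are logistic and Cox. The first estimates an odds ratio for a binary response and the second a hazard ratio for a time to event. Neither estimates a difference in change of a score, which is what 3.4.1 asks for.

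5. **Which time point is the randomised contrast?** 3.4.1 says end of treatment without naming a week. Under 3.1 and 3.3.3.4, treatment lasts 12 weeks, group A then leaves the trial, and group B moves to postbiotics for a further 12 weeks. Week 12 is the only point at which A on postbiotics can be compared with B on placebo as randomised.

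6. **Are the data for that contrast collected?** Yes. The flowchart in 3.3.3 has SGA-7, the quality-of-life scale, GSRS, EFS and the anthropometric measures at Follow-up 2 and again at week 12.

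7. **Is Follow-up 2 before allocation?** The text is unclear. The last item of 3.3.3.1 randomises patients who are eligible after screening. 3.3.3.2 lists randomisation again, in the introduction period in which the baseline measures are taken. On the first reading the baseline follows allocation.

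**The case against.** **Much of this could be left to an SAP.** That is true of the choice between ANCOVA, change scores and ordinal methods, and of any cut for logistic regression. The SGA-7 and EFS bands in Appendices A and D could be cut, so logistic regression is not ruled out. It is not true of the normal population or the Cox model, which are stated analyses that do not fit the design.

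**Normal population may be a slip for the control group.** The test list does not settle this. One-way ANOVA suits three groups, but the independent t test named first suits two, and both sit in a generic list. The sentence does set the normal population against the patients in both groups, which makes a slip less likely. Slip or not, the sentence needs correcting.

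**The trial calls itself exploratory (3.6).** It still names primary outcomes and applies P < 0.05, so the contrast should be explicit. The exploratory aim does limit how serious the point is.

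A reader might infer more than the text supports:

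- *That the protocol has replaced the A-versus-B comparison.* The exposure sentence may be meant as treated versus control, and the listed t and non-parametric tests would be valid if applied to A versus B. What can be said is that the comparison is never clearly stated.
- *That 3.8 inflates the false-positive rate for treatment.* Any such rate would need a hypothetical normal group of assumed size and assumed distance from the patients. A three-group ANOVA that rejected because normals differ from dialysis patients would be rejecting correctly. It would become a false claim about treatment only through a further misreading, which the protocol does not state.
- *That P < 0.1 screening determines the primary estimate.* 3.8 does not say that the multivariate model is the primary analysis, and it also admits covariates on clinical grounds. The risk is conditional: if the rule were applied to the treatment effect, the data would choose which adjusted estimate is reported.

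**Conclusion.** The point holds and should be fixed. Section 3.8 does not clearly state the primary comparison of 3.4.1, sets the patients against a population that is neither enrolled nor sourced, plans a P5 limit that no outcome uses, and names Cox regression when none of the six outcome entries is a time to event.

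Its size is that of an internal inconsistency: following 3.8 to the letter does not produce the A-versus-B difference in change. It rests on the protocol's wording alone and on no numerical assumption. It does not undermine the design, because the randomised comparison remains available and its data are already scheduled. The missing binary outcome for logistic regression and the P < 0.1 rule are secondary.

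**What to change.** In 3.8, delete the normal-population comparison, the P5 limit and Cox regression. If any of these is really intended, name the reference source or define the event and censoring in 3.4. Then state:

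> *For the outcomes of 3.4.1, group A is compared with group B at week 12, adjusted for the baseline value of the same measure, and the difference is given with a 95% CI.*

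- Use ANCOVA for roughly continuous scores, and an ordinal or rank-based baseline-adjusted version for the single 1-7 SGA rating.
- Do not choose covariates for this treatment effect by P < 0.1.
- Keep logistic regression only for a binary outcome that 3.4 names.

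Baseline adjustment is an improvement: an unadjusted A-versus-B test on change would also be valid. The baseline should precede allocation, so 3.3.3.1 and 3.3.3.2 must be reconciled on when randomisation takes place.

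The cost is a wording change in 3.8 and that clarification in 3.3.3. No new data are needed. How the several measures in 3.4.1 share the 0.05 level is a separate matter that this change does not settle.

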3.3.3.2 Introduction Period (-2nd to 0 week before the randomization)

The second follow-up visit should be on the first hemodialysis day of the week (e.g. Monday or Tuesday). The following list summarizes the procedures for the introduction period:

- We should record the most recent URR and spKt/V of patients within last 1 month prior to the randomization.
- We should record any change of medications after the last follow-up visit.
- We should record the diet of patients.
- We should score the rating scales listed in the flowchart above.
- We should perform the anthropometric measurements listed in the flowchart above.
- We should collect the results of recent routine blood test before dialysis of the patient.
- We should collect the blood and stool samples for urotoxins and intestinal flora baseline measurements.
- The patients will be divided randomly into treatment group and control group. Patients in the treatment group will be given oral intestinal flora metabolites 3 times a day and 1 bag each time. Patients in the control group will be given placebo.
- The therapeutic medications should be supplied.

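### Section 3.8 names no linear model that adjusts for the baseline value and does not say whether week-12 scores or changes are compared, which costs precision in a 60-patient trial

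*Protocol*

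**What the plan says.** Protocol section 3.8 treats questionnaire scores, anthropometry, biochemistry and urotoxins as continuous variables. Its group comparisons are "Independent t test, Chi-square test /Fisher exact test, one-way ANOVA and non-parametric analysis". The sentence containing that list sets a normal population beside the two patient groups, so it does not clearly specify an arm-against-arm test. The only regression models named are logistic and Cox. Their covariates are general clinical data, variables associated with the outcome, and variables passing a univariate screen at P<0.1. The baseline value of the outcome is not named. The threshold is P<0.05, which "is considered statistically significant. All confidence intervals are stated at the 95% confidence level".

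Section 3.4 words the outcomes as changes. For one of the two primary outcomes it reads "Changes of quality of life from the baseline to the end of treatment and differences between the intervention group and the placebo group", and the nutritional primary outcome and the secondary outcomes take the same form.

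Baseline data are collected. At the introduction visit (section 3.3.3.2) the instruction is "We should score the rating scales listed in the flowchart above", and anthropometry, blood and stool are taken at that visit too. Section 3.3.3.3 repeats these measurements at week 12.

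On size, patients are "randomly divided into group A and group B in a 1:1 ratio", and section 3.6 says that "a sample size of 30 per group is planned for this study".

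**The concern.** Each numeric outcome has a value before treatment and a value at week 12. Three simple arm comparisons are available: the week-12 score alone, the change, or the week-12 score (or change) with the baseline value as a covariate. Section 3.8 does not choose between the first two and names no method for the third.

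The covariate-adjusted models that it does name do not fit these outcomes. Logistic regression needs a two-class outcome and Cox regression needs a time to an event. Section 3.4 defines neither.

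What is at stake is precision. Section 3.6 plans 30 patients per arm. If 24 per arm complete, the difference in baseline means that arises by chance has a standard deviation of √(2/24) = 0.29 SD units (√(2/30) = 0.26 with all 30). A week-12 comparison ignores that difference. A change score removes it by subtracting the full baseline difference, which over-corrects whenever the correlation between the two visits is below 1. A baseline covariate corrects by the amount that the data support.

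**Working it through.** **The plan's own figure.** Section 3.6 states that "the sample size of each group should be 20" and then: "Taking into consideration the dropout rate of 20% by the end of the study". Inflating 20 gives 20/(1 − 0.20) = 25, or 20 × 1.20 = 24 by the cruder rule. Neither gives the planned 30, which would need a dropout of one third. The 20 itself cannot be rebuilt, because no effect size, SD or power is given. This mismatch is a separate matter. What is used here is the number of completers: 30 × (1 − 0.20) = 24 per arm.

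**Inputs.**
- Completers: 24 per arm (section 3.6), 1:1 allocation (section 3.1).
- Significance level: 0.05 (section 3.8). Sidedness is not stated; two-sided is assumed.
- Power: 80%, assumed as a yardstick.
- Correlation r between baseline and week-12 values: not in the document; 0.3 to 0.8 shown.
- Equal SDs at the two visits and approximate normality: assumed.

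**Variance of the arm difference**, relative to a t test on the week-12 score alone:
- week-12 score only: 1
- change score: 2(1 − r)
- ANCOVA on baseline: 1 − r²

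ANCOVA relative to change is (1 − r²)/[2(1 − r)] = (1 + r)/2, so the variance saved is (1 − r)/2.

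**Detectable difference.** For a two-sample t test with 24 per arm, two-sided 5% and 80% power, the detectable difference is 0.826 SD (noncentral t; the normal approximation gives 0.81). Multiply by √[2(1 − r)] for change and by √(1 − r²) for ANCOVA. The degree of freedom spent on the covariate is negligible here.

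| r | ANCOVA / change variance | Detectable, change (SD) | Detectable, ANCOVA (SD) | Extra patients the change score needs for equal precision |
|---|---|---|---|---|
| 0.3 | 0.65 | 0.826 × √1.4 = 0.98 | 0.826 × √0.91 = 0.79 | 1/0.65 − 1 = 54% |
| 0.5 | 0.75 | 0.826 × √1.0 = 0.83 | 0.826 × √0.75 = 0.72 | 1/0.75 − 1 = 33% |
| 0.7 | 0.85 | 0.826 × √0.6 = 0.64 | 0.826 × √0.51 = 0.59 | 1/0.85 − 1 = 18% |
| 0.8 | 0.90 | 0.826 × √0.4 = 0.52 | 0.826 × √0.36 = 0.50 | 1/0.90 − 1 = 11% |

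If week-12 scores alone were tested, the detectable difference would be 0.83 SD whatever r is. ANCOVA would then save r² of the variance: 9% at r = 0.3, 25% at 0.5 and 64% at 0.8.

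**One power figure.** At r = 0.6 and an assumed true difference of 0.7 SD, a change-score t test has about 76% power and ANCOVA about 84%.

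**The case against.** Five points can be made for the plan.

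1. *Baseline is used.* A reader might infer from section 3.8 alone that the baseline scores are ignored. Section 3.4 does not support that: it defines the outcomes as changes from baseline. The fair comparator is therefore the change-score t test, and the week-12-only figures apply only if the tests were run that way, which section 3.8 leaves open. This point stands.

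2. *The multivariate step could admit baseline.* Variables associated with the outcome may enter, and the baseline value is an obvious candidate. It is neither excluded nor assured, and it could enter only a logistic or Cox model, so the gap for numeric scores remains.

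3. *Logistic regression need not mean a large loss.* A reader might infer that scores will be cut at the median, with a steep fall in power. The protocol mentions no median split. The classes that it gives are the bands for SGA-7 and EFS in its appendices, and it does not say that they are used to compare arms. No figure for such a loss is claimed here.

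4. *This is an efficiency preference, and the trial calls itself exploratory.* A change-score t test in a randomised trial is valid, and at high r little is gained. Both are true. But section 3.8 still tests at P<0.05 with 95% confidence intervals, and a small trial benefits from precision that costs nothing.

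5. *Covariate adjustment is normally left to a SAP.* A SAP not shown here might add ANCOVA. The point rests on what section 3.8 itself states: it lists its methods, and the adjusted models on that list do not suit the outcomes in section 3.4.

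**Conclusion.** The point holds as one of precision and clarity. Section 3.8 leaves open whether week-12 scores or changes are compared, and names no linear model with a baseline covariate. The only covariate-adjusted models that it names do not fit numeric scores with no defined event.

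Against the change-score analysis that section 3.4 implies, ANCOVA would cut the variance by 35% at r = 0.3 and by 10% at r = 0.8. The gain is substantial if the scores correlate weakly over 12 weeks and small if they are stable. The direction holds for any r between 0 and 1; the size rests on the assumed r, equal SDs, approximate normality and 24 completers per arm.

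A reader might go further and infer that the planned comparison is biased or invalid. The documents do not support that: a t test on change between randomised arms is valid, only less precise. The change is worth making, but the trial does not depend on it.

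**What to change.** State in section 3.8 that each numeric outcome at week 12 (or its change) is compared between arms by linear regression (ANCOVA), with arm and the baseline value of that outcome as covariates, and that the adjusted difference is reported with its 95% confidence interval. The two forms give the same arm estimate once baseline is in the model, so this also settles the question of score or change. Add that logistic and Cox regression are not used for the arm comparison of numeric scores.

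The cost is analysis wording only. Baseline values are already collected at the introduction visit, and the SPSS and R versions named in section 3.8 fit the model. No visit, sample or patient is added.
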